3.1.5. Criteria for Dose Escalation

Compared to the traditional mTPI method, the proposed mTPI method for this protocol includes stopping rules and dose escalation/finding criteria, which prevents the target DLT rate to reach $\geq 33\%$ for determining the MTD. This proposed mTPI method, targeting a DLT rate of 27.5% and an acceptable DLT interval (22.5% to 32.5%), will be utilized in Part 1 dose escalation/finding phase, and will also be used to monitor the DLTs so as not to cross toxicity boundaries in the expansion of a cohort. In this process, the upper limit of the DLT rate to determine a MTD will be $< 33\%$. This proposed mTPI method is more conservative than the traditional toxicity probability interval (TPI) method.

The mTPI method relies upon a statistical probability algorithm, calculated using all patients treated in the current dose level to determine one of the following dose-finding decisions: the subsequent dose should be escalated, maintained at the current dose, or de-escalated in the next cohort of 1-4 patients, or the trial should be terminated (Table 1).

Table 1. Dose Escalation/De-Escalation Decision Rules

DLT	n=2	n=3	n=4	n=5	n=6	n=7	n=8	n=9	n=10	n=11	n=12
0	E	E	E	E	E	E	E	E	E	E	E
1	S	S	S	S	E	E	E	E	E	E	E
2	D	D	D	S	S	S	S	S	S	S	E
3		U	U	D	D	S	S	S	S	S	S
4			U	U	U	U	D	S	S	S	S
5				U	U	U	U	U	D	S	S
6					U	U	U	U	U	U	U
7						U	U	U	U	U	U
8							U	U	U	U	U
9								U	U	U	U
10									U	U	U
11										U	U
12											U

Actions to be taken: D = De-escalate the dose; E = Escalate the dose; S = Stay at the dose. U = Unacceptable toxicity.

Initially, dose cohorts may consist of 1-2 patients in the single agent dose escalation in Part 1A. When a DLT is observed, additional patients will be enrolled and dose escalation decision will follow the mTPI criteria. Table 2 showing escalating doses with a 100% to 150% increase from the previous dose in dose levels (DLs). In later cohorts it is anticipated that total daily dose level increases may approximate 100% or less depending on emerging available clinical data, including safety/tolerability, laboratory, PK and PD findings.

The total daily dose will be administered once a day (QD) or in divided doses of either two (BID) or three times a day (TID).

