Initial dose levels are provided in Table 2 and intermediate dose levels may be considered as indicated. Intra-patient dose escalation for patients enrolled in dose level 1 and 2 may be considered in consultation with the sponsor. Once the respective dose level has been declared safe, patients who have completed at least 2 Cycles of treatment at the original enrolled dose level may escalate to the next higher dose level that has cleared the DLT observation period of 28 days.

Table 2. PF-06873600 Dose Levels (Immediate Release Formulation)

DOSE LEVEL (DL)*	DOSE	TOTAL DAILY DOSE***
DL 1**	1 mg BID	2 mg
DL 2	2 mg BID	4 mg
DL 3	5 mg BID	10 mg
DL 4	10 mg BID	20 mg
DL 5 and Beyond		Escalation to continue to the MTD or desired pharmacological activity

*The proposed doses, schedule(s), and PK time points may be reconsidered or amended during the study based on the emerging safety and PK data. Intermediate doses may be considered when deemed necessary based on on-going evaluation of safety and toxicity data.

** Starting dose DL1.

*** Total daily dose may be administered in up to 3 divided doses.

In principle, all patients must be evaluated for a minimum DLT observation period of 28 days in Part 1. However, in order to be evaluable for DLT assessment patients need to have received at least 75% of planned doses unless the patient has experienced a DLT prior to receiving 75% of the planned dose.

The dose escalation in Part 1A, and 1C, dose finding in Part 1B, and each arm of the dose expansion in Part 2 of the study will stop as the applicable following criteria are met:

- The maximum sample size has been achieved (approximately 75 patients in Part 1, excluding patients enrolled in biomarker cohorts, and approximately 70 patients in Part 2);

- 6 to 12 evaluable patients (for Parts 1A, Part 1B, and Part 1C) that have been enrolled at a PF-06873600 dose level (as a single agent, in combination with letrozole, and in combination with fulvestrant, each) that is predicted to be the MTD per the mTPI method;
- All dose levels explored appear to be overly toxic, and the MTD cannot be determined.

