9.2. Statistical Methods and Properties

9.2.1. Statistical Methods for Dose Escalation/De-Escalation

Many alternative designs have been proposed to the standard 3+3 design for Phase 1 dose escalation studies that improve its accuracy, efficiency and statistical validity.

The traditional mTPI design (Ji et al., 2010)²⁹ uses a Bayesian statistics framework and a beta/binomial hierarchical model to compute the posterior probability of 3 dosing intervals that reflect the relative difference between the toxicity rate of each dose level to the target rate ($p_T = 0.275$). If the toxicity rate of the currently used dose level is far smaller than p_T , the mTPI will recommend escalating the dose level; if it is close to target probability (p_T), the mTPI will recommend continuing at the current dose; if it is far greater than p_T , the mTPI will recommend de-escalating the dose level. These rules are conceptually similar to those used by the 3+3 design, except the decisions of an mTPI design are based on posterior probabilities calculated under a coherent probability model. The proposed modified TPI method for this protocol includes stopping rules and dose escalation/finding criteria, which prevents the target DLT rate to reach $\geq 33\%$ for determining the MTD. This proposed mTPI method is more conservative than the traditional TPI method. Being a rule-based design, mTPI automatically and appropriately tailors dose-escalation and de-escalation decisions for different studies with different toxicity parameters. More importantly, all the dose-escalation and de-escalation decisions for a given study can be pre-calculated under the mTPI design and presented in a two-way table (See [Section 3.1.5](#)). Thus, compared to other advanced model-based designs published in the literature, the mTPI design is logistically less complicated and easier to implement. Recently, a Phase 1 study based on the mTPI design has been published (Fanale, 2011).³⁰

Decision rules are based on calculating unit probability mass (UPM) of 3 dosing intervals corresponding to under, proper, and over dosing in terms of toxicity. Specifically, the underdosing interval is defined as $(0; p_T - e_1)$, the over-dosing interval $(p_T + e_2, 1)$, and the proper-dosing interval $(p_T - e_1, p_T + e_2)$, where e_1 and e_2 are small fractions. Based on the safety profile of PF-06873600 as a single-agent in study (C3661001), e_1 is selected as

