The dose finding process in Part 1 using mTPI is designed to establish the MTD defined as the highest dose that yields a target of approximately 27.5% probability of DLT and considers equivalent doses that yield probability of DLT in the interval (Equivalence Interval) of (22.5%, 32.5%). The 27.5% target was chosen based on safety considerations and is considered appropriate based on simulations performed on other Pfizer Phase 1 study protocols (ie, B7831001, PF-06671008) and expert input. The prior distribution of DLT is set as a beta (0.5,0.5) and the threshold probability for early termination and dose exclusion is set to 0.95 as suggested in the original mTPI method (Ji et al., 2010).²⁹ A modification of the mTPI could be applied for dose levels that are tested in more than 6 patients: a decision to increase the dose could be made only if the observed DLT rate is <22.5% (2 DLT out of 10 Patients) and a decision to test more patients at a dose only if the DLT rate is below 32.5%. In addition, doses with an incidence of DLT, eg, 4 out of 10, or apparently higher than 32.5% cannot be selected as MTD, even though it might be allowed by the mTPI method.

Cohorts of patients could receive doses already tested but a dose that is associated with decision to “Dose de-escalate, unacceptable toxicity” cannot be revisited and no more patients should be treated at this dose or higher doses for the remainder of the trial.

The maximum sample size for Part 1 would be approximately N=75 for the dose escalation/finding safety cohorts and N=6 to 12 for the biomarker cohorts but actual sample size will depend on the underlying dose toxicity profile and variability in actual data realization.

The study will continue accruing until one of the three stopping conditions below is triggered.

The algorithm will stop if any of the following criteria is met:

1. The maximum sample size has been achieved;
2. MTD has been identified with sufficient accuracy: 6 to 12 patients have been accumulated on a dose that is currently estimated to be the MTD/RDE; or

3. All doses explored appear to be overly toxic and the MTD cannot be determined.

Due to binomial data variability in small samples, DLTs may be observed in a first cohort(s) by chance even when the true Probability (DLT) is fairly low. This could result in the estimated posterior DLT rate to exceed the targeted 27.5% very early in the trial.

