Appendix 2. Detailed Dose Escalation/De-Escalation Scheme for mTPI Design

Escalation/De-escalation algorithms for total number of patients treated at the current dose level (current and previous cohorts)

- With 2 patients treated at current dose level:
 - 0 DLT -> escalate;
 - 1 DLT -> remain at the same dose;
 - 2 DLTs -> de-escalate and consider current dose as intolerable.

- With 3 patients treated at current dose level:
 - 0 DLT -> escalate;
 - 1 DLT -> remain at the same dose;
 - 2 DLTs -> de-escalate;
 - 3 DLTs -> de-escalate and consider current dose as intolerable.

- With 4 patients treated at current dose level:
 - 0 DLT -> escalate;
 - 1-2 DLTs -> remain at the same dose;
 - 3-4 DLTs -> de-escalate and consider current dose as intolerable.

- With 5 patients treated at current dose level:
 - 0 DLT -> escalate;
 - 1-2 DLTs -> remain at the same dose;
 - 3 DLTs -> de-escalate;
 - 4-5 DLTs -> de-escalate and consider current dose as intolerable.

- With 6 patients treated at current dose level:
 - 0-1 DLT -> escalate;
 - 2 DLTs -> remain at the same dose;
 - 3 DLTs -> de-escalate;

- 4-6 DLTs -> de-escalate and consider current dose as intolerable.
- With 7 patients treated at current dose level:
 - 0-1 DLT -> escalate;
 - 2-3 DLTs -> remain at the same dose;
 - 4 DLTs -> de-escalate;
 - 5-7 DLTs -> de-escalate and consider current dose as intolerable.
- With 8 patients treated at current dose level:
 - 0-1 DLT -> escalate;
 - 2-3 DLTs -> remain at the same dose;
 - 4 DLTs -> de-escalate;
 - 5-8 DLTs -> de-escalate and consider current dose as intolerable.
- With 9 patients treated at current dose level:
 - 0-1 DLT -> escalate;
 - 2-4 DLTs -> remain at the same dose;
 - 5-9 DLTs -> de-escalate and consider current dose as intolerable.
- With 10 patients treated at current dose level:
 - 0-1 DLT -> escalate;
 - 2-4 DLTs -> remain at the same dose;
 - 5 DLTs -> de-escalate;
 - 6-10 DLTs -> de-escalate and consider current dose as intolerable.
- With 11 patients treated at current dose level:
 - 0-1 DLT -> escalate;
 - 2-5 DLTs -> remain at the same dose;
 - 6-11 DLTs -> de-escalate and consider current dose as intolerable.

- With 12 patients treated at current dose level:
 - 0-2 DLTs -> escalate;
 - 3-5 DLTs -> remain at the same dose;
 - 6 DLTs -> de-escalate;
 - 7-12 DLTs -> de-escalate and consider current dose as intolerable.

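### At 4/9, 4/10, 4/11 and 5/11 the dose-finding grids print Stay, although on safety-cohort data the dose can no longer qualify as MTD; the rule that would stop further enrolment there is only optional

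*Protocol*

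**What the plan says.** Protocol 9.2.1 says that the method "includes stopping rules and dose escalation/finding criteria, which prevents the target DLT rate to reach" 33% or more when the MTD is determined. Protocol 3.1.5 makes the same claim and adds: "In this process, the upper limit of the DLT rate to determine a MTD will be" below 33%.

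Protocol 9.2.2 carries two rules on high observed rates.

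- **Selection, mandatory.** A dose with, for example, 4 DLTs in 10 patients, "or apparently higher than 32.5% cannot be selected as MTD, even though it might be allowed by the mTPI method".
- **Allocation, optional.** "A modification of the mTPI could be applied for dose levels that are tested in more than 6 patients". Under that modification, more patients are tested at a dose only while its DLT rate is below 32.5%.

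The three grids (Protocol Table 1, Protocol Appendix 2, SAP Table 2) contain neither rule. All print Stay at 4/9, 4/10, 4/11, 5/11, 4/12 and 5/12. Appendix 2, for example, has "2-4 DLTs -> remain at the same dose" at both 9 and 10 patients.

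The MTD stopping criterion has no rate cap. Protocol 9.2.2 stops when "6 to 12 patients have been accumulated on a dose that is currently estimated to be the MTD/RDE". Protocol 3.1.5, SAP 2.1.4 and SAP 4.2.1 ask for 6 to 12 evaluable patients at a dose "that is predicted to be the MTD per the mTPI method". The SAP repeats neither the selection bar nor the optional allocation rule.

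**The concern.** The grid is what a team uses to place the next cohort. In four cells it directs more patients to a dose that the selection bar has already ruled out, because no run of DLT-free patients within the 12-patient limit brings the rate back under 32.5%. The only mandatory limit takes effect at selection, after those patients have been treated. Two teams working from the same protocol could also act in opposite ways at 4/9: one follows the printed Stay, the other applies the optional rule and enrols nobody.

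**Working it through.** **Inputs.** Target 27.5% and interval (0.225, 0.325): Protocol 3.1.5 and 9.2.1. Prior Beta(0.5, 0.5): Protocol 9.2.2, where "the threshold probability for early termination and dose exclusion is set to 0.95"; SAP 4.2.1 prints 0.975. At most 12 patients per dose: Protocol 9.3.1. Cohort sizes of 2 to 4: Protocol 3.1.7 for Parts 1B and 1C (Part 1A also allows 1).

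**Reproducing the grid.** After x DLTs in n patients the posterior is Beta(0.5 + x, 0.5 + n − x). The unit probability mass (UPM) is the posterior probability of an interval divided by its length, so the divisors are 0.225, 0.10 and 0.675. The largest UPM sets the action.

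| x/n | Observed | UPM under | UPM proper | UPM over | Pr(rate > 27.5%) | Best finish at n = 12 |
|---|---|---|---|---|---|---|
| 4/9 | 44.4% | 0.291 | 1.521 | 1.159 | 0.871 | 4/12 = 33.3% |
| 4/10 | 40.0% | 0.435 | 1.991 | 1.042 | 0.815 | 4/12 = 33.3% |
| 4/11 | 36.4% | 0.606 | 2.428 | 0.920 | 0.754 | 4/12 = 33.3% |
| 5/11 | 45.5% | 0.186 | 1.359 | 1.218 | 0.905 | 5/12 = 41.7% |
| 4/12 | 33.3% | 0.802 | 2.804 | 0.799 | 0.688 | at the limit |
| 5/12 | 41.7% | 0.281 | 1.801 | 1.121 | 0.863 | at the limit |

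Stay has the largest UPM in all six rows, so in these cells the printed grid is plain mTPI output with no cap added. Pr(rate > 27.5%) stays below both 0.95 and 0.975, so the exclusion rule does not act either. At 4/9, 4/10 and 4/11, Stay allows 3, 2 and 1 more patients; at 5/11 it allows 1; at 4/12 and 5/12 it adds none.

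**Chance of reaching one of the four cells at one dose.** This is an exact binomial recursion through the Stay cells. It assumes enrolment on every Stay, no return after Escalate or De-escalate, and the optional rule not applied.

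With cohorts of 3 the only path is 1/3, 2/6, 4/9, with probability [3p(1−p)²]² × 3p²(1−p):

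- p = 0.275: 0.4336² × 0.1645 = 0.031
- p = 0.33: 0.4444² × 0.2189 = 0.043
- p = 0.40: 0.432² × 0.288 = 0.054

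With cohorts of 2 only 4/10 can be reached. Under Table 1 the path is 1/2, 1/4, 2/6, then 2/8 or 3/8, then 4/10, with probability [2p(1−p)]² × (1−p)² × 5p²(1−p)². That is 0.017 at p = 0.275 and 0.024 at p = 0.40. Appendix 2 prints Stay at 2/4 where Table 1 prints De-escalate. This opens a second, equally likely route to 2/6 and doubles the results to 0.033 and 0.048.

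Cohorts of 4 pass through n = 4, 8 and 12 only and reach none of the four cells.

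| Grid | Cohorts | True rate 27.5% | True rate 40% |
|---|---|---|---|
| Table 1 | 3 | 3.1% | 5.4% |
| Table 1 | 2 | 1.7% | 2.4% |
| Table 1 | highest of 36 orderings | 7.5% | 10.7% |
| Appendix 2 | 2 | 3.3% | 4.8% |
| Appendix 2 | highest of 36 orderings | 12.0% | 17.2% |
| Either | 4 | 0% | 0% |

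The 36 orderings are all sequences of cohorts of 2, 3 or 4 that add to 12. The highest values go through 4/10 (3+4+3+2 for Table 1, 4+3+3+2 for Appendix 2). They are upper values, because some of their paths pass through counts below 32.5%, such as 2/7, at which stopping from 6 patients would already be allowed.

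**The case against.** The strongest reply is that 9.2.2 already deals with this. Its modification covers dose levels with more than 6 patients, and all the cells in question have 9 or more. If it is applied, no further patients enter at these counts and every chance above becomes zero. A reader might infer that 9.2.2 limits high rates only at selection; the allocation rule shows otherwise. What stands against the reply is that the rule is only something that could be applied, and the documents a team would use to allocate patients do not show it.

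A reader might also infer that 3.1.5 and 9.2.1 promise a 33% cap on every Stay decision, or that the plan could declare a barred MTD. Neither is supported. Both sections state the limit for determining the MTD. The selection bar meets it and openly says that the mTPI result may differ. The SAP describes itself as a supplement to the protocol, so its silence does not lift the bar.

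Three further limits are fair. Stay at 4/12 and 5/12 adds no patients. Stopping is allowed from 6 patients, and a safety review team oversees dosing, so a team need not enrol on every Stay. In Parts 1A and 1C, 9.2.2 also uses biomarker-cohort safety data to establish the MTD or RDE, so a dose that fails on safety-cohort data could in principle be recovered there.

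**Conclusion.** The point holds as one about allocation. At 4/9, 4/10, 4/11 and 5/11 the grids direct 1 to 3 more patients to a dose that cannot finish below 32.5% on safety-cohort data, and the only rule against it is optional. This is strict in Part 1B, where the MTD/RDE rests on safety cohorts and 6 to 12 patients (Protocol 3.1.2 and 9.2.2). In Parts 1A and 1C it covers safety-cohort data only.

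The size is small: a few per cent per dose for equal cohorts of 2 or 3, and nil for cohorts of 4. These are chances of extra allocation, not of a wrong MTD. They rest on assumed cohort sizes and true rates, on enrolment at every Stay, and on the optional rule not being used. Practical reach is limited: Protocol Appendix 7.1 reports no DLTs at the single-agent IR RDE, and Appendix 8 records the sponsor's decision of 07 September 2022 to terminate. The documents give no DLT counts for the MR or combination regimens.

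**What to change.** Print De-escalate at 4/9, 4/10, 4/11 and 5/11 in Protocol Table 1, Protocol Appendix 2 and SAP Table 2, and at 4/12 and 5/12 for consistency only. Add a condition that the observed DLT rate is below 32.5% to the MTD stopping criterion in Protocol 3.1.5 and 9.2.2 and SAP 2.1.4 and 4.2.1.

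Making the optional rule mandatory would also work, but it would close 3/7, 3/8 and 3/9 as well (42.9%, 37.5% and 33.3%). Those can still reach 3/12 (25%), so that step is the sponsor's choice and is not needed here.

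The cost is table and text edits, and no eligible MTD is lost on safety-cohort data. The one downside is in Parts 1A and 1C, where a biomarker cohort of about 6 with few DLTs could have lowered the pooled rate: 4/12 plus 0/6 or 1/6 gives 4/18 = 22.2% or 5/18 = 27.8%, and 5/12 plus 0/6 gives 27.8%. One more DLT in either case gives 6/18 = 33.3%. Protocol 3.1.1 opens a biomarker cohort only once the dose is cleared for escalation or is the MTD, so this loss is unlikely.

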9.3. Sample Size Determination

9.3.1. Part 1

In Part IA, Part IB, and Part IC patients will participate in a dose escalation/finding phase aimed at estimating the MTD. The sample size for this component of the study will vary depending on the number of DLTs observed.

Approximately 75 patients are expected to be enrolled in the dose escalation/finding safety cohorts and an additional 6-12 patients are expected in the biomarker cohorts in Parts IA and IC. The actual number of patients enrolled will depend on the tolerability of PF-06873600 and the number of dose levels required to identify the MTD/RDE. Part IA, Part IC and each independent combination cohort in Part IB (PF-06873600 in combination with letrozole and PF-06873600 in combination with fulvestrant) can be stopped and MID declared with approximately 6 to 12 patients. As for the number of patients treated at each dose, it is expected to be at 1 to 4 patients for the doses actually studied. However, since variable cohort size is allowed, the actual number of patients treated at each dose (including MTD) will vary from 1 to 12.

9.3.2. Part 2

Part 2, the expansion aims will be conducted to assess efficacy as well as safety and tolerability of PF-06873600 in single agent and combination therapy. The sample sizes for Part 2 are determined based on published historical data as benchmark data, I-sided type 1 error rate of $\alpha = 0.1$ with 80% power or higher. Approximately 100 patients are expected to be enrolled in Part 2. Enrollment of participants into a given cohort may be discontinued if minimal or no anti-tumor activity is observed. CCI

I

[REDACTED]

I [REDACTED]

I [REDACTED]

9.4. Efficacy Analysis

In this First In Patient study anti-tumor activity is a primary objective for Part 2 of the study. Tumor response will be presented in the form of patient data listings that include, but are not limited to, tumor type, starting dose, tumor response at each visit, and best overall response. In addition, progression date, death date, date of first response and last tumor assessment date, and date of last contact will be listed. Objective response rate (ORR), progression-free survival (PFS), overall survival (OS), time to progression (TTP), and duration of response (DoR) will be summarized and presented if data permits.

The definition of each response category is provided in [Appendix 4](#) (RECIST 1.1).

9.5. Analysis of Pharmacokinetics and Pharmacodynamics

9.5.1. Analysis of Pharmacokinetics

9.5.1.1. Single-Dose and Steady-State PF-06873600 Pharmacokinetic Analysis

Plasma concentrations of PF-06873600 will be summarized descriptively (n, mean, standard deviation, CV, median, minimum, maximum, geometric mean and its associated CV) by dose, cycle, day, and nominal time.

Plasma concentration-time data within a dose interval after the morning dose on Cycle 1, Day 1 (for patients of Part 1A and 1B), Cycle 1, Day 15 (for all patients, with exception of the MR formulation selection cohort) or for patients of the MR formulation selection cohort, plasma concentration-time data after Day -7 and Day -4, respectively, will be analysed for individual patients using noncompartmental methods. The noncompartmental analysis will estimate PK parameters including the following:

1. Cycle 1 Day 1 (and also Lead-in Day -7 and Day -4 for patients of the MR formulation selection cohort within Part 1C): the maximal concentration (C_{max}), time to maximum plasma concentration (T_{max}), and area under the plasma concentration versus time curve from time 0 to the last sampling time point within the dose interval (AUC_{last}), and if data permit, area under the plasma concentration versus time curve from time 0 extrapolated to infinity (AUC_{inf}), terminal elimination half-life ($t_{1/2}$), apparent oral plasma clearance (CL/F), apparent volume of distribution (V_z/F);
2. Cycle 1 Day 15: steady state C_{max} ($C_{max,ss}$), T_{max} , AUC within one dose interval ($AUC_{\tau,ss}$), minimum plasma concentration ($C_{min,ss}$), oral CL (CL_{ss}/F), and if data permit, apparent volume of distribution (V_{ss}/F), $t_{1/2}$, and accumulation ratio (R_{ac}).

The single-dose and steady-state PK parameters will be summarized descriptively (n, mean, standard deviation, coefficient of variation (CV), median, minimum, maximum, geometric mean and its associated CV) by dose, cycle and day.

Dose normalized AUC_{inf} (AUC_{τ} at steady state), AUC_{last} and C_{max} will be plotted against dose (using a logarithmic scale) by cycle and day. These plots will include individual patient values and the geometric means for each dose. These plots will be used to help understand the relationship between the PK parameters and dose.

